**Effectiveness results:**

Assessment of lip fullness included subjects with a baseline MLFS score of 1 or 2. Scoring was based on visual live assessment by the Investigator. Results of the assessment at Baseline, Week 4 and Week 12 are presented in Table 10. All subjects in the ITT population had a clinically significant improvement, i.e. at least one grade improvement from baseline for the upper lip, and the majority (49/51 [96%]) of lower lips were improved at 12 weeks.

**Table 10: MLFS by visit - ITT population**

MLFS	Baseline				4 weeks				12 weeks			
	Upper lip		Lower lip		Upper lip		Lower lip		Upper lip		Lower lip	
	n	%	n	%	n	%	n	%	n	%	n	%
1 – Very thin	26	48.1	22	40.7	0	0.0	1	1.9	0	0.0	2	3.9
2 – Thin	28	51.9	32	59.3	4	7.5	2	3.8	8	15.7	3	5.9
3 – Medium	0	0.0	0	0.0	24	45.3	13	24.5	29	56.9	25	49.0
4 – Full	0	0.0	0	0.0	17	32.1	29	54.7	12	23.5	19	37.3
5 – Very Full	0	0.0	0	0.0	8	15.1	8	15.1	2	3.9	2	3.9
Total (N)	54	100.0	54	100.0	53	100.0	53	100.0	51	100.0	51	100.0

% = n/N\*100

Further, the Investigator evaluated the degree of improvement from baseline in the visual appearance of the subject's lips using the 7-point non-validated GAIS at Weeks 4 and 12. Improvement (defined as "Improved", "Much improved" or "Very much improved") was noted for the upper and lower lips combined at Weeks 4 and 12 (98.1% and 98.0%, respectively).

**Table 11: Investigator assessment of improvement using GAIS - ITT population**

GAIS Investigator assessment	4 weeks				12 weeks			
	Upper lip		Lower lip		Upper lip		Lower lip	
	n	%	n	%	n	%	n	%
Very Much Improved	34	64.2	45	84.9	23	45.1	32	62.7
Much Improved	12	22.6	6	11.3	13	25.5	13	25.5
Improved	6	11.3	2	3.8	14	27.5	6	11.8
No Change	1	1.9	0	0.0	0	0.0	0	0.0
Worse	0	0.0	0	0.0	1	2.0	0	0.0
Much Worse	0	0.0	0	0.0	0	0.0	0	0.0
Very Much Worse	0	0.0	0	0.0	0	0.0	0	0.0
Total (N)	53	100.0	53	100.0	51	100.0	51	100.0

% = n/N\*100

Subjects also rated improvement of their lip fullness, relative to pretreatment appearance, using the GAIS at Weeks 4 and 12. For the upper and lower lips combined, the proportion of subjects that assessed themselves as improved or better from baseline was 94.3% at Week 4, and 84.3% at Week 12.

**HOW SUPPLIED**

*Restylane Silk* is supplied in a disposable glass syringe with a luer-lock fitting.

*Restylane Silk* is co-packed with sterilized needle(s) 30 G x ½" as indicated on the carton. A patient record label is a part of the syringe label. Remove it by pulling the flap marked with three small arrows. This label is to be attached to patient records to ensure traceability of the product.

The contents of the syringe are sterile.

The volume in each syringe and needle gauge is as stated on the syringe label and on the carton.

**SHELF LIFE AND STORAGE**

*Restylane Silk* must be used prior to the expiration date printed on the package. Store at a temperature of up to 25° C (77° F). Do not freeze. Protect from sunlight.

Refrigeration is not required.

Do not resterilize *Restylane Silk* as this may damage or alter the product.

Do not use if the package is damaged. Immediately return the damaged product to Galderma Laboratories, L.P.

Rx only

U.S. PATENT 5,827,937; 8,455,459; 8,778,909; 8,357,795; 8,450,475; 8,822,676

#### DIRECTIONS FOR ASSEMBLY

[figure not shown]
For safe use of *Restylane Silk*, it is important that the needle/blunt cannula is properly assembled.

Hold the syringe on the ribbed part (C) of the white closure system (luer-lock adapter). With your other hand, take hold of the white cap (A) at the end of the closure system and gently tilt back and forth carefully until cap disconnects and can be pulled off (seal will be broken). Do not rotate. Do not touch the syringe tip (B) to keep it sterile.

#### ASSEMBLY OF NEEDLE TO SYRINGE

Use the thumb and forefinger to hold firmly around both the glass syringe barrel and the luer-lock adapter. Grasp the needle shield (or hub if using a cannula) with the other hand. To facilitate proper assembly, both push and rotate firmly.

#### PRE-TREATMENT GUIDELINES

Prior to treatment, the patient should avoid taking aspirin, nonsteroidal anti-inflammatory medications, St. John's Wort, or high doses of Vitamin E supplements. These agents may increase bruising and bleeding at the injection site.

#### TREATMENT PROCEDURE

1. It is necessary to counsel the patient and discuss the appropriate indication, risks, benefits and expected responses to the *Restylane Silk* treatment. Advise the patient of the necessary precautions before commencing the procedure.

2. Assess the patient's need for appropriate anesthetic treatment for managing comfort, i.e., topical anesthetic, local or nerve block.
3. The patient's face should be washed with soap and water and dried with a clean towel. Cleanse the area to be treated with alcohol or another suitable antiseptic solution.
4. Sterile gloves are recommended while injecting *Restylane Silk*.
5. Before injecting, press rod carefully until a small droplet is visible at the tip of the needle.
6. When using needle, after insertion, and just before injection, the plunger rod should be withdrawn slightly to aspirate and verify that the needle is not intravascular.
7. *Restylane Silk* is administered using a thin gauge needle (30 G x 1/2") or as an alternative a blunt tip cannula (recommended gauge sizes 25-27G) can be used. Please note use of a cannula is intended for lip augmentation only whereas needles may be used to treat both lips and perioral rhytids.
8. When using a needle, the needle is inserted at an approximate angle of 30° parallel to the length of the wrinkle, fold, or lip. For rhytids, *Restylane Silk* should be injected into the mid-to-deep dermis. *Restylane Silk* should be injected into the submucosal layer for lip augmentation, care should be taken to avoid intramuscular injection. If *Restylane Silk* is injected too superficially this may result in visible lumps and/or bluish discoloration. When using a cannula for lip augmentation, an entry point is made in the skin, e.g. with a sharp needle of appropriate size. Inject slowly.
9. Inject *Restylane Silk* applying even pressure on the plunger rod. It is important that the injection is stopped just before the needle is pulled out of the skin to prevent material from leaking out or ending up too superficially in the skin.
10. Only correct to 100% of the desired volume effect. Do not overcorrect. With cutaneous deformities the best results are obtained if the defect can be manually stretched to the point where it is eliminated. The degree and duration of the correction depend on the character of the defect treated, the tissue stress at the implant site, the depth of the implant in the tissue and the injection technique.
11. Typical usage for each treatment session is specific to the site as well amount of augmentation or rhytids correction desired. Based on U.S. clinical studies, the maximum recommended dose per treatment is 1.5 mL per lip per treatment or 1.0 mL for perioral rhytid correction.

[figure not shown]
#### INJECTION TECHNIQUES

1. *Restylane Silk* can be injected by a number of different techniques that depend on the treating physician's experience and preference, and patient characteristics.
2. **Serial puncture (only recommended for needle) (A)** involves multiple, closely spaced injections along wrinkles or folds. Although serial puncture allows precise placement of the filler, it produces multiple puncture wounds that may be undesirable to some patients.
3. **Linear threading (includes retrograde and antegrade) (B)** is accomplished by fully inserting the needle/cannula into the middle of the wrinkle or fold and injecting the filler along the track as a "thread." Although threading is most commonly practiced after the needle/cannula has been fully inserted and is being withdrawn, it can also be performed while advancing the needle/cannula ("push-ahead" technique). To enhance the vermillion of the lip, the retrograde linear threading technique is the most advisable.
4. Serial threading is a technique that utilizes elements of both approaches

**Note! The correct injection technique is crucial for the final result of the treatment.**

**A. Serial Puncture (only recommended for needle)**

**B. Linear Threading (includes retrograde and antegrade)**

5. Dissection of the sub-epidermal plane with lateral movement of the needle, rapid flows ( $\geq 0.3$  mL/min), rapid injection or high volumes may result in an increase in short-term episodes of bruising, swelling, redness, pain, or tenderness at the injection site.
6. When the injection is completed, the treated site should be gently massaged so that it conforms to the contour of the surrounding tissues. If an overcorrection has occurred, massage the area firmly between your fingers or against an underlying area to obtain optimal results.
7. If so called “blanching” is observed, i.e., the overlying skin turns a whitish color, the injection should be stopped immediately and the area massaged until it returns to a normal color. Blanching may represent a vessel occlusion. If normal skin coloring does not return, do not continue with the injection. Treat in accordance with the American Society for Dermatologic Surgery guidelines, which include hyaluronidase injection.
8. If the wrinkles or lips need further treatment, the same procedure should be repeated until a satisfactory result is obtained. Additional treatment with *Restylane Silk* may be necessary to achieve the desired correction.
9. If the treated area is swollen directly after the injection, an ice pack can be applied on the site for a short period. Ice should be used with caution if the area is still numb from anesthetic to avoid thermal injury.
10. Patients may have mild to moderate injection site reactions, which typically resolve in less than 18 days in the lip.

**STERILE NEEDLE(S)**

Follow national, local or institutional guidelines for use and disposal of medical sharp devices. Obtain prompt medical attention if injury occurs.

- To help avoid needle breakage, do not attempt to straighten a bent needle. Discard it and complete the procedure with a replacement needle.
- Do not reshield used needles. Recapping by hand is a hazardous practice and should be avoided.

- Discard unshielded needles in approved sharps collectors.
- *Restylane Silk* is provided with a needle that does not contain engineered injury protection. Administration of *Restylane Silk* requires direct visualization and complete and gradual insertion of the needle making engineered protections infeasible. Care should be taken to avoid sharps exposure by proper environmental controls.

Listing 16.2.6.2.3 – Derived Primary and Secondary Efficacy Responses on Overall LFGS and Overall POL for Per-Protocol Population.....	80
Listing 16.2.6.2.4 – Derived Other Efficacy Responses Based on Observed Data: LFGS and POL for Upper/Lower Lip	81
Listing 16.2.7.1.1 – Adverse Events (Related to Vascular Injections/Visual Events).....	82
Listing 16.2.7.1.2 – Adverse Events (Excluding Vascular Injections/Visual Events).....	83
Listing 16.2.7.2.1 – Adverse Events (Related to Vascular Injections/Visual Events) Leading to Study Treatment Interrupted/Discontinued	83
Listing 16.2.7.2.2 – Adverse Events (Excluding Vascular Injections/Visual Events) Leading to Study Treatment Interrupted/Discontinued	83
Listing 16.2.7.3.1 – Serious Adverse Events (Related to Vascular Injections/Visual Events).....	83
Listing 16.2.7.3.2 – Serious Adverse Events (Excluding Vascular Injections/Visual Events).....	83
Listing 16.2.7.4 – Adverse Events (Related to Vascular Injections/Visual Events) Lasted more than 30 Days	83

Statistical Analysis Plan

1 Purpose of Statistical Analysis Plan

The purpose of the statistical analysis plan is to describe in detail all the data, statistical methods, and summary tables required to implement the statistical analysis of Clinical Study Protocol PRO 2018-02 (Section 8 in the study protocol version 4.0, dated October 02, 2018).

This plan has also incorporated responses to the FDA review comments on the Abbreviated SAP version 2.0, two consideration points in particular as follows:

- (1) Use of As-Treated (AT) population for safety instead of Intent-to-Treat population
- (2) For the primary efficacy endpoint, due to the likeliness that there will be a large number of ties in the ranked data, use the Wilcoxon Mann-Whitney test and the associated confidence interval for the median differences to test the non-inferiority hypothesis.

2 Study Objectives

To compare the safety and efficacy profile of PN40082 versus Restylane Silk Injectable Gel with 0.3% lidocaine (Restylane Silk) for lip augmentation.

3 Study Design and Sample Size Determination

3.1 Study Design

For the purpose of exploring the above objectives, the study will be conducted as a multicenter, double-blind, randomized, controlled study in subjects seeking lip augmentation. Subjects will be randomized 1:1 to treatment with either PN40082 or Restylane Silk. The treating investigator will be performing assessments at baseline to confirm inclusion/exclusion criteria entry. The Evaluating Investigator and subject will be blinded to the treatment. Injections of the study device will be performed by an unblinded Treating Investigator. At each visit, the blinded Evaluating Investigator and subject evaluations of the treated areas will be performed and recorded. Visits will occur at:

- Visit 1 / Week 0 (Day 1) – baseline and treatment
- Visit 2 / Day 28 (± 2 days) / Month 1 – interim visit (touch-up if necessary)
- Visit 3 / Day 56 (± 4 days) / Month 2 – interim visit
- Visit 4 / Day 84 (± 4 days) / Month 3 – interim visit
- Visit 5 / Day 168 (± 7 days) / Month 6 – End of Study (EOS) Visit. All subjects will undergo the consent procedure for the open-label retreatment protocol.

Telephone contacts for safety follow-up will occur at:

- Day 3 (± 2 days) - Safety follow-up telephone call
- Day 14 (± 2 days) – Safety follow-up telephone call
- Day 33 (± 2 days) – Safety follow-up telephone call (for subjects with touch-up treatment)
- Day 44 (± 2 days) – Safety follow-up telephone call (for subjects with touch-up treatment)
- Day 112 (± 4 days) / Month 4 – Safety follow-up telephone call
- Day 140 (± 4 days) / Month 5 – Safety follow-up telephone call

Evaluations include:

- Lip Fullness Grading Scale (LFGS) (Overall lip fullness considering both lips together, fullness of the upper lip and fullness of the lower lip)

- Perioral lines at rest severity scale (POL) (Overall perioral lines at rest severity considering both lips together, perioral lines at rest severity of the upper lip and perioral lines at rest severity of the lower lip)
- Patient Global Aesthetic Improvement (pGAI)
- Investigator Global Aesthetic Improvement (iGAI)
- Swelling Assessment
- Subject Satisfaction with Lips Assessment (using VAS)

Safety will be assessed by monitoring adverse events (AEs) and concomitant medications at all study visits. Other Safety evaluations include lip function, lip sensation, lip texture, lip firmness, lip symmetry and lip movement/function. Other evaluations include Investigator Ease of Use Assessment.

At Visit 5, subjects and blinded evaluating investigators will be asked which treatment they thought was administered as a way of evaluating the blinding.

3.2 Sample Size Determination

For the PRO 2018-02 study, the primary variable is change from baseline to Month 3 in LFGS. The sample size was determined based on: (1) both PN40082 and Restylane Silk having an equal mean value with a common standard deviation of 0.85 for change from baseline in LFGS, and (2) the non-inferiority limit of -0.50. The test:control ratio of 1:1 results in 126 (63:63) per-protocol (PP) subjects at power of 90%. A total of 158 subjects will be randomized to obtain 126 (63:63) PP subjects assuming that 80% of randomized subjects meet the PP criteria.

4 Populations To Be Analyzed

Three subject populations are defined as follows:

- (1) As-treated (AT) (safety population): All randomized subjects who received study device. AT subjects will be included in the safety analysis for the treatment they actually received.
- (2) Modified intent-to-treat (mITT): All randomized subjects who met the inclusion/exclusion criteria, and received study device.
- (3) Per-protocol (PP): All randomized subjects who met all inclusion/exclusion criteria; received study device; completed Visit 5/Month 6 within the specified window; had overall LFGS score by the Blinded Evaluating Investigator at Visit 3/Month 2 within the specified visit window; and had no significant protocol violations that would affect the treatment evaluation.

For the purpose of determining the PP status of the subject, "significant protocol violations" are any unforeseen events that occurred during the conduct of the trial that result in noteworthy study protocol violations that could have possibly interfered with the therapeutic administration of the treatment or the precise evaluation of treatment efficacy.

Efficacy analyses will be performed on the mITT and PP populations, with PP as the primary population and mITT supportive. Analyses of safety and other evaluations will be performed on the AT population.

5 Planned Analyses

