#### Analysis Populations:

Intent-to-treat (ITT/safety) population: All randomized subjects who received study device

Modified intent-to-treat (mITT): All randomized subjects who met the inclusion/exclusion criteria, were randomized, and received study device

Per-protocol (PP): All randomized subjects who met all inclusion/exclusion criteria; received study device, completed Visit 5 within the specified window; had LFGS score by the Blinded Evaluating Investigator at Visit 3/Month 2 within the specified visit window, and had no significant protocol violations that would affect the treatment evaluation

Efficacy analyses will be performed on the mITT and PP populations, with PP as the primary population and mITT supportive.

Safety analyses will be performed on the ITT population.

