### 7.3.3 Subject Withdrawal Criteria

A subject may withdraw from the study at any time for any reason.

A subject will be withdrawn from the study if his/her safety or well-being is determined to be at risk. Withdrawal will be made at the discretion of the investigator or at the subject's request.

A subject must withdraw from the study for any of the following reasons:

- The subject or legal representative withdraws consent
- The subject's study device assignment is unblinded
- There is a significant protocol violation as determined by the Sponsor or medical monitor.

A subject may be withdrawn from the study for any of the following reasons:

- Lost to follow-up
- Investigator discretion

Withdrawal is permanent; after a subject has been withdrawn, he/she will not be allowed to enroll again.

If a subject is withdrawn from the study for any reason, the EOS or Early Termination procedures (Visit 5/Month 6) should be completed and any outstanding data and subject diaries should be collected. Data, including the date and primary reason for withdrawal, must be documented on the EOS case report form (CRF) and source document.

If a subject withdraws from the study at any time due to an AE, the reason for withdrawal, the nature of the AE, and its clinical course must be fully documented. The investigator must strive to follow the subject until the AE has resolved, become clinically insignificant, is stabilized, or the subject is lost to follow-up. For any SAE, follow the procedures provided in Section 7.9.7.

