### **7.5 Study Schedule**

The visit-by-visit schedule of study activities is provided in Section 2. The timing of each visit is relative to Day 1, which is defined as the day the subject is randomized and first treated.

All visits should be performed within the windows specified on the schedule of study activities. Every attempt should be made to have each subject attend each visit as scheduled. If a subject is unable to attend a visit within the specified window the visit should be scheduled as closely as possible to the applicable window.

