#### **7.9.4 Pregnancy**

Pregnancies occurring after administration of study device require immediate reporting. They must be reported within 24 hours after the investigator has become aware of the pregnancy. A pregnancy report will be completed and sent by fax to the Sponsor or designee within 24 hours of becoming aware of the pregnancy. The investigator will collect follow-up information regarding the outcome of the pregnancy and any postnatal sequelae in the infant that must also be reported to the Sponsor or designee. Upon awareness of the outcome of the pregnancy, the Principal Investigator or designee must forward a follow-up Pregnancy Report with any relevant information to the Sponsor or designee.

If the outcome of the pregnancy meets the criteria for immediate classification of an SAE (e.g., spontaneous abortion, stillbirth, neonatal death, or congenital anomaly), the investigator will report the

event by faxing a completed SAE report form to the Sponsor or designee within 24 hours of being notified of the pregnancy report.

The subject should immediately be withdrawn from the study.

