##### **7.9.10.2 Unblinding Treatment for a Subject During the Study**

Unblinding by the investigator should occur only in the event of an AE or SAE for which it is necessary to know the study treatment to determine an appropriate course of therapy for the subject. In the event of an emergency that requires breaking of the study blind, the Investigator can unblind the subject without prior contact with the Medical Monitor although the Investigator will immediately notify the Medical Monitor accompanied by a written explanation of the reason why the blind was broken. In the event of an emergency that requires breaking of the study blind, the randomization code will be maintained by each unblinded Treating Investigator that can be opened to reveal the study device to the applicable staff. In the event the unblinded Treating Investigator is not available, the site should designate another unblinded staff member not involved in the study conduct to access the randomization code for that

subject. Note this can be done WITHOUT informing the blinded Evaluating Investigator and thus maintaining the study blind. If unblinding occurs, the subject must be withdrawn from the study.

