5.2 Handling of Dropouts or Missing Data

For demographics, baseline characteristics, safety profile and other evaluations, each variable will be analyzed using the existing data. Subjects with missing data will be excluded only from the analyses for which data are not available.

No missing values will be replaced in the PP analyses. There will not be missing data for the primary efficacy endpoint for the PP population based on the PP definition in Section 4.

Only for the overall LFGS and its derivatives for the mITT analysis, missing scores will be replaced using the multiple imputation (MI) approach for the mITT analysis only. Depending on the pattern of missingness, a two-step process may be employed. If missing data occur for an intermediate visit, they will be imputed first via a Markov Chain Monte Carlo (MCMC) method. As a result, a monotone missingness pattern will be obtained for the data to be fully imputed. The subsequent imputation will use Monotone Regression to produce 5 imputed datasets where the remaining missing data are filled in.

When missing overall LFGS score at a given visit is imputed, the values from all its previous visits will be included as predictor in the imputation model. For example, for a subject with missing overall LFGS at Visit 4, the overall LFGS scores from Visits 1 through 3 for the subjects will be included in the imputation model. Other variables that go into the imputation models include treatment, site, and key baseline characteristics of age, gender, race and Fitzpatrick skin type.

To prepare for MI, for subjects who are early discontinued from the study, their efficacy data captured at the termination visit will be assigned to the nearest corresponding scheduled visit.

The SAS code for MI is as follows, using the random number 69833 as the seed for the first Step and 192185 as the seed for the second step. Where notation of main variables:

- Trt = treatment: 1 for Test product, 2 for competitor product
- Invid = site number
- Age = subject's age

- Sexn = gender: 1 for female, 2 for male
- Nrace = race: 1 for White, 2 for Asian, 3 for Native Hawaiian or Other Pacific-Islander, 4 for Black or African American, 5 for American Indian or Alaska Native, 6 for Other, 7 for Mixed
- Fstn = Fitzpatrick skin type in numeric value
- v1 - v5: LFGS at Visits 1-5 accordingly

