5.5.1 Primary Efficacy Analysis

The primary efficacy endpoint is change from baseline to Visit 3/Month 2 in overall LFGS. The null hypothesis to be tested is that the Test device is inferior to the Control device. The results for PP are considered as definitive and those for mITT as supportive.

Summary statistics (mean, SD, minimum, median, maximum) and 95% confidence interval (CI) for mean will be presented for the changes scores for each treatment.

Due to the fact that the change scores would only contain 5 possible values (0, 1, 2, 3, and 4), the normal distribution assumption is hardly attainable, and therefore, the nonparametric Hodges-Lehmann (HL) estimators will be employed to test the study hypothesis. The 95% confidence limits for the median differences between the two treatment groups (PN40082 minus Restylane Silk) will be derived using PROC NPARIWAY with the option for the HL estimators. If the lower limit is on or above -1.0, the null hypothesis will be rejected to support the claim that PN40082 is non-inferior to Restylane Silk.

For the mITT analysis, the above analysis will be carried out for each copy of the MI data sets. Then PROC MIANALYZE will be performed to account for the between and within variation in the multiply imputed data sets.

To assist an assessment for the consistency of the treatment effect among sites, summary of the primary endpoint will be presented by site for the primary population (i.e., the PP subjects).

The primary endpoint will also be analyzed for the following two subsets of the PP subjects: (1) subjects that have injection on one lip only, and (2) subjects that have injections on both lips.

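### The definitive per-protocol set for the Month 2 primary endpoint also requires an in-window Month 6 visit, so valid Month 2 scores can be dropped because of something that happens later

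*SAP*

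**What the plan says.** SAP section 4 lists the PP conditions jointly: eligibility, receipt of device, "completed Visit 5/Month 6 within the specified window; had overall LFGS score by the Blinded Evaluating Investigator at Visit 3/Month 2" in its own window, and no significant protocol violation. The Protocol synopsis and section 8.1 carry the same pair of visit conditions: "completed Visit 5 within the specified window; had LFGS score by the Blinded Evaluating Investigator at Visit 3/Month 2 within the specified visit window". Visit 3 is Day 56 ± 4 days and Visit 5 is Day 168 ± 7 days.

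SAP 5.5.1 places the primary endpoint at Visit 3/Month 2 and ranks the two analyses: "The results for PP are considered as definitive and those for mITT as supportive". SAP 5.2 adds: "There will not be missing data for the primary efficacy endpoint for the PP population based on the PP definition in Section 4".

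SAP Table 14.1.4 has a row for Visit 5 not completed in window. Its footnotes define significant protocol violations as the events that exclude a subject from any analysis population, and count a subject with several violations under each one.

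Neither document gives a reason for the Visit 5 condition or defines a separate PP set for Month 2.

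**The concern.** A Month 2 score is fixed once the blinded evaluator has recorded it. Under the PP definition, whether it counts in the deciding analysis still depends on conduct up to about Day 168. The documents show several ways for a subject to have a valid Month 2 score and then fail on Visit 5:

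- **Late visit.** Protocol 7.5 says that if a window cannot be met, "the visit should be scheduled as closely as possible to the applicable window". A site that follows this instruction still loses the subject from PP.
- **Withdrawal after Month 2.** On pregnancy, Protocol 7.9.4 says "The subject should immediately be withdrawn from the study". On unblinding, Protocol 7.9.10.2 says "If unblinding occurs, the subject must be withdrawn from the study".
- **Early termination visit.** After any withdrawal, Protocol 7.3.3 says "the EOS or Early Termination procedures (Visit 5/Month 6) should be completed". Held at the time of withdrawal, that visit normally falls outside Day 168 ± 7.

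Two things are at stake. Precision is lost if usable scores are discarded. The comparison is biased if the subjects lost after Month 2 had different Month 2 results from those who stayed, and if this differs between arms.

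**Working it through.** **1. The plan's own figure.** Inputs from SAP 3.2 and Protocol 8.5 and 8.2: SD 0.85, margin -0.50, true difference 0, lower limit of a two-sided 95% interval, 90% power, 80% of randomized subjects in PP.

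- Normal approximation: n per arm = 2 × [0.85 × (1.960 + 1.282) / 0.50]² = 60.7, so 61. The noncentral t gives 62. The plan uses 63, where noncentral-t power is 90.6%.
- Inflation: 126 / 0.80 = 157.5, so 158.

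The sample size reproduces. The issue is the population definition, not the arithmetic.

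**2. Is the condition needed for complete primary data?** PP separately requires an in-window Visit 3 score. That criterion alone makes the SAP 5.2 statement true. The Visit 5 condition adds nothing to it.

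**3. Precision.** The allowance for non-PP subjects is 158 - 126 = 32. The documents do not say how many of these would fail on Visit 5 alone, so the range is 0 to 32. Half-width = t(0.975, 2n - 2) × 0.85 × √(2/n).

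| Share of the 32 recovered | n per arm | Power, margin -0.50 | 95% half-width |
|---|---|---|---|
| none | 63 | 90.6% | 0.300 |
| half | 71 | 93.6% | 0.282 |
| all (upper bound) | 79 | 95.7% | 0.267 |

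**4. Bias, by formula (assumed inputs).** If a fraction f of the Month-2-valid subjects in one arm is removed, and they score d grades below that arm's remaining subjects, the arm mean rises by f × d. With f = 0.10 and d = 0.5 the shift is 0.05 grade. At 63 per arm the standard error is 0.85 × √(2/63) = 0.151. If the shift is in the PN40082 arm, the chance of claiming non-inferiority at a true difference of -0.50 is Φ(0.05/0.151 - 1.96) = 5.2%, against 2.5% with no shift.

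**5. Bias, by simulation (assumed inputs).** Integer change scores with SD 0.85; 75 per arm with a valid Month 2 score; 3, 5 or 10 per arm then lost. Selective leavers score about 0.5 to 0.97 grade below stayers, and in the one-arm cases the other arm loses the same number at random. The table shows false non-inferiority at true -0.50, with a t interval and margin -0.50.

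| Lost per arm | Selective in PN40082 only | Selective in control only | Selective in both |
|---|---|---|---|
| 3 | 3–5% | 1.4–1.8% | about 3% |
| 5 | 4–7% | 0.9–1.2% | about 3% |
| 10 | 7–14% | 0.3–0.8% | 2–3% |

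With everyone kept, or with purely random loss, the rate is 2–3%. At true 0 with 10 lost per arm, power is about 95% with everyone kept, 91–92% with random loss and 73–82% with control-only selective loss.

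**6. The same loss under the SAP 5.5.1 rule** (Hodges-Lehmann lower limit on or above -1.0), 10 lost per arm. At true 0 and -0.50 non-inferiority is claimed in 100% of runs in every scenario. At true -1.0 the claim rate is 94–95% with all kept, 96–99% with PN40082-only loss and 75–81% with control-only loss. The difference between the two margins is a separate issue.

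**The case against.** The strongest case against has four parts.

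- **The supportive analysis keeps these scores.** The mITT set has no Visit 5 condition, and the full primary analysis is repeated on it. This is true, but mITT does not decide the result. It also differs from PP by every PP-only exclusion at once, so a gap between the two could not be traced to Visit 5.
- **The affected subjects can be identified.** A reader might infer from Table 14.1.4, which counts overlapping violations, that they cannot. That is not so. Listing 16.2.1.1 gives each subject's reason for exclusion from PP, Listing 16.2.1.3 gives the study day of each visit, and Table 14.1.2 gives discontinuation reasons by arm. SAP 5.3 also compares PP with non-PP subjects at baseline. These outputs allow a count, but they do not return the scores to the definitive analysis.
- **The harm is conditional.** This stands. Every bias figure above rests on assumed loss counts, selectivity and arm imbalance. Subjects and evaluators are blinded, and Protocol 7.2 invites in-window completers into an open-label retreatment study; both may limit selective loss. Equal loss leaves almost no bias. Under the SAP rule the conclusion did not move at true 0 or -0.50.
- **Power is already budgeted.** This also stands. The 80% allowance covers all the PP criteria, so the precision gain may be zero.

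In addition, withdrawal for pregnancy or unblinding can occur at any time. Before Visit 3 it may leave no Month 2 score to lose, so only later withdrawals belong to this point.

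**Conclusion.** The point holds as a flaw of definition. The set that decides a Month 2 question is conditioned on a visit scheduled 168 - 56 = 112 days after the endpoint visit, without a stated reason and without need for complete primary data. It should be corrected, because the condition gives the primary analysis no identifiable benefit and can only remove valid scores.

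The recoverable number is 0 to 32 of 158 subjects, with power at most 95.7% instead of 90.6% under the planning assumptions. The size and direction of any bias are unknown.

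Three stronger readings are not supported:

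- **That the PP analysis is biased towards non-inferiority.** Selective loss of poor responders from PN40082 would act that way, but the same loss from control would act against it.
- **That the trial is underpowered because of the condition.** The planned 63 per arm already allows for it.
- **That all violations must be cut off at Visit 3.** The Table 14.1.4 footnote makes the Visit 5 row a consequence of the PP condition, so changing that condition is enough.

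**What to change.** Before unblinding:

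1. For the Month 2 primary analysis, delete the in-window Visit 5 condition from the PP definition (SAP 4; Protocol synopsis and 8.1), and do not treat a missed Visit 5 window as a significant protocol violation for that analysis. Leave the other significant-violation rules as they are.
2. Keep the in-window Visit 5 condition for all Month 6 PP results: Table 14.2.2.4 and the Visit 5 parts of Tables 14.2.3.1, 14.2.3.2, 14.2.3.3, 14.2.3.6 and 14.2.3.7.
3. State which PP flag the Month 3 endpoints use.
4. Report, by arm, the number of subjects who fail PP only on Visit 5, for example as an added row in Table 14.1.4.
5. Repeat the primary analysis without those subjects as a sensitivity analysis. Because nothing else in the definition changes, this reproduces the current PP analysis exactly.

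**Cost.** No new data are needed, and the Month 2 PP set cannot shrink. The programming needs a second PP flag, with edits to the outputs that now assume a single flag (among them Tables 14.1.1, 14.1.3, 14.1.4, 14.1.5.3 and 14.1.5.6, and Listings 16.2.1.1 and 16.2.6.2.3). The Month 2 and Month 6 PP counts may differ and will need a footnote. The protocol revision needs Sponsor and IRB approval under Protocol 10.5.
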